#### 2.4.2. Analysis of Tissue Samples

Soft tissue punch biopsies (3 mm) were taken after wound debridement sessions at week zero (day 0) and week six (day 42). After tissue collection, samples were immediately transported to the laboratory for cellular proliferation and microbiological analyses.

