## 2.4. Intervention

2.4.1. DFU Debridement and Wound Management Patients were randomly assigned to receive either surgical debridement or UAW debridement every week during a six-week treatment period. All debridement procedures were performed by the same surgeon ([name]), who is a specialist in the field of diabetic foot surgery with more than 21 years of experience.

Surgical debridement involved removal of all necrotic and devitalized tissue that was incompatible with healing, as well as surrounding callus.

UAW debridement was performed using an UAW SONOCA 185 device (Söring GmbH, Quickborn, Germany) by a senior clinician ([name]) with more than three years of experience applying this type of debridement. The UAW device is equipped with three UAW instruments with different sonotrode shapes and generates an ultrasound low frequency of 25 kHz. The choice of sonotrode depends on ulcer depth (ranges from superficial to deep). The UAW device piezoelectrically transforms the electrical energy delivered from the UAW device into mechanical oscillations in the sonotrode tip. In the majority of diabetic foot ulcers in the UAW group, a two-minute treatment with 40% intensity was made by holding the sonotrode in contact mode, holding it perpendicular to the wound bed and moving it across in an up-and-down pattern. For diabetic foot ulcers measuring  $> 15 \text{ cm}^2$ , the debridement treatment was increased to three minutes. In addition to UAW debridement, a scalpel was used for careful tissue removal, but only in cases where periwound tissue exhibited calluses or maceration.

Between debridement sessions, sterile saline was used to clean all wounds prior to evaluation and all patients received standard of care for their diabetic foot ulcers, which consisted of moist wound dressings for wound management and proper off-loading (a removable walker cast based on the functioning and ambulatory status of the patient) as per the International Working Group of the Diabetic Foot guidelines [1,20]. When necessary, patients with moderate infections took empirical antibiotics during the treatment period, based on IDSA guideline recommendations [14], until the results from deep tissue culture were available [21]. After we received tissue culture results, we adjusted the antibiotic therapy to target the bacteria that were isolated during tissue culture.

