#### 2.5.3. Third Outcome Measure: Evaluation of Wound Conditions

Diabetic foot ulcers were evaluated at patient admission and weekly before and after each debridement treatment. A validated wound scoring system was used to assess the wound bed tissue according to quality, presence and consistency of granulation tissue [25]. Furthermore, diabetic foot ulcers were evaluated for amounts of wound exudate and periwound skin conditions such as skin maceration by the same senior clinician ([name]) according to the triangle wound assessment [26].

Wound healing was supervised weekly during the treatment period (6 weeks) and the wound size was assessed using Visitrak (Smith & Nephew, Hull, UK), determining the area of the lesion with an approximation of  $\pm 5 \text{ mm}^2$ .

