#### 2.7. Sample Size

Granmov.12 program (Municipal Institute of Medical Research, Barcelona, Spain) (<https://www.imim.cat/ofertadeserveis/software-public/granmo/>) was used to calculate the sample size. Thus, we analyzed 51 patients (24 in surgical group and 27 in UAW group) with a statistical power of 0.80 and an alpha of 0.05, with a

power of the clinical difference of 37% to detect a statistically significant between groups.

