## 2.8. Randomization

A computer-generated random number table was used to carry out the randomization of the patients into the two groups by an investigator who was unaware of the identity of the participants.

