## 2.10. Statistical analysis

Data were analyzed, based upon an intention-to-treat analysis, using the software package SPSS for iOS version 21.0 (SPSS, Inc. Chicago, IL, USA). Kolmogorov-Smirnov test was used to verify the assumption of normality of all continuous variables. Chi-square test was performed to calculate differences between groups and, if applicable, Fisher's exact test for categorical variables. Student's t-test and Mann-Whitney U test were performed for normally and abnormally distributed quantitative variables, respectively. Graphics to evaluate the differences among decrease in bacterial load and cellular proliferation between groups were done using GraphPad® for Mac OS.

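### Does taking week-0 tissue after a debridement session, with no stated contrast in section 2.10, undermine the tissue comparisons?

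*Combined protocol and SAP*

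**What the plan says.** Section 2.4.1 makes the debridement method the randomized treatment: "Patients were randomly assigned to receive either surgical debridement or UAW debridement every week during a six-week treatment period". Section 2.4.2 says the punch biopsies "were taken after wound debridement sessions at week zero (day 0) and week six (day 42"), and the same samples serve the main outcome (CD31, collagen and actin scores) and the secondary outcome (CFU/g). For the clinical wound ratings, section 2.5.3 separates the two sides of a session: "Diabetic foot ulcers were evaluated at patient admission and weekly before and after each debridement treatment".

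Section 2.8 describes the method of allocation ("A computer-generated random number table was used to carry out the randomization of the patients into the two groups") but not its timing relative to the first session. Section 2.2 measures eligible wound area once the wound has been debrided, so a debridement at or before entry is possible.

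Section 2.10 assigns tests by type of variable. For categorical data, "Chi-square test was performed to calculate differences between groups", with Fisher's test where needed. For the rest, "t-test and Mann-Whitney U test were performed for normally and abnormally distributed quantitative variables". It attaches no time point, change score or covariate to these tests. Its only hint is in the sentence on figures: "Graphics to evaluate the differences among decrease in bacterial load and cellular proliferation between groups". Section 2.7 gives the numbers: "we analyzed 51 patients (24 in surgical group and 27 in UAW group").

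**The concern.** A baseline value is protected by randomization only if it is taken before the allocated treatment. Read literally, the week-0 biopsy follows a session, and that session may be the first allocated one. The wound ratings are made on both sides of a session and the tissue is not, so no pre-session sample exists to fall back on.

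If surgical and ultrasound debridement remove different amounts of bacteria at once, the arms already differ at week 0. Change from week 0 then subtracts that difference from the week-6 result and could hide a real effect or produce an apparent one. Because section 2.10 names no contrast, a reader cannot tell whether the reported comparison is exposed to this. The mention of a decrease in bacterial load suggests that it might be. The plausible case is CFU/g. The documents point to no immediate shift in the 0–3 histology scores.

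**Working it through.** **Inputs.** From section 2.7: 24 and 27 patients (24 + 27 = 51) and alpha 0.05, taken here as two-sided because sidedness is not stated. The documents give no SD, no week-0 to week-6 correlation and no immediate arm difference. The following are therefore assumptions: SD 1.5 log10 CFU/g at each visit, correlation ρ = 0.3, 0.5 or 0.7, a true week-6 difference of 1.0 log10 where there is an effect, and an immediate difference of 0.5 log10 where there is one. No figure in the plan bears on this point, so there is none to reproduce.

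**Formulae.** Let D0 and D6 be the expected arm differences in week-0 and week-6 tissue, and k = √(1/24 + 1/27) = 0.2805.

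- Week-6 test: contrast D6, standard error 1.5 × k = 0.421.
- Change test: contrast D6 − D0. SD 1.5 × √(2(1 − ρ)) = 1.775, 1.500, 1.162; standard error 0.498, 0.421, 0.326.
- Week 6 adjusted for week 0: contrast D6 − ρD0. Residual SD 1.5 × √(1 − ρ²) = 1.431, 1.299, 1.071.

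Rejection rates come from the noncentral t distribution. The adjusted null rates in case A are simulated.

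**Type of result under no cumulative effect.** Entries are for ρ = 0.3/0.5/0.7.

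| Case | Week 6 | Change | Adjusted |
|---|---|---|---|
| A. D0 = 0.5, D6 = 0 | 5% | 17/21/32% | 7/10/20% |
| B. D0 = 0.5, D6 = 0.5 | 21% | 5% | contrast 0.5(1 − ρ) = 0.35/0.25/0.15 |

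Case A alone looks like a false-positive problem for change. Yet week-6 tissue is also taken after a session. Case A therefore needs the immediate difference to be present on day 0 and to have vanished, or been exactly offset, by day 42. Case B, where each session has the same immediate effect and nothing accumulates, is at least as natural, and it reverses the ranking. Neither test is wrong: the week-6 comparison includes that day's session, and change isolates what accumulates if the immediate difference is the same at both visits.

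Small immediate differences matter little. In case A with D0 = 0.2, the change test rejects in 7–9% of trials and the adjusted test in 5–7%.

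**Power when D6 = 1.0.**

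| Share of effect already present at week 0 | Week 6 | Change | Adjusted |
|---|---|---|---|
| None | 64% | 50/64/85% | 69/77/90% |
| 20% | 64% | 35/46/67% | 63/68/80% |

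Making unadjusted week-6 values the main analysis would give up power in most of these cells. The adjusted analysis is ahead throughout the first row. With 20% of the effect already present it is one point behind at ρ = 0.3 and ahead at 0.5 and 0.7. The price is some attenuation: with D0 = 0.2 the adjusted contrast is 1 − 0.2ρ = 0.94, 0.90, 0.86 instead of 1.0.

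**Main 0–3 scores.** Assume no immediate shift, a latent standardized difference of 0.8 and four equal categories. Mann-Whitney power is then 71–72% on week-6 scores and 50/61/78% on change. The better choice depends on a correlation that the documents do not give.

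**The case for a change.** The strongest case for acting is that the plan separates pre- and post-session ratings for the wound but has no pre-session tissue, is silent on when allocation happened, and leaves both the quantity and the test open. Similar week-0 values in the two arms would not settle the matter. At SD 1.5 the 95% interval for the week-0 arm difference is about ±2.01 × 0.421 = ±0.85 log10, too wide to rule out 0.5. Adjustment for week 0 does not fully remove the problem either, as the 20% entry in case A shows.

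Three things stand. Section 2.10 does not state the contrast. If the biopsy followed the first allocated session, change in CFU/g means change after that session. A reader who took week 0 as untreated tissue would then misread the figures.

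The rest does not carry over into a change of plan. The documents do not describe the week-0 tissue as untreated; section 2.4.2 says openly that it follows a session. The week-0 session may have been a common entry debridement, in which case the arms are expected to be alike there and week 0 is a sound covariate. Rank testing of the 0–3 scores is already available through the Mann-Whitney test in section 2.10. Sections 2.7 and 2.10 also describe the data as already analysed, so a contrast written in now would be post hoc.

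**Conclusion.** The concern describes the text accurately but identifies no error. Sampling is symmetric and disclosed. The contrasts differ in expectation only if the first allocated session preceded the biopsy and acted unequally in the two arms; the documents establish neither condition. Where the contrasts do differ, each answers its own question. Under the assumed SD of 1.5, an immediate 0.5 log10 difference gives 17–32% rejection on change in one scenario and 21% on week-6 values in the mirror scenario. Imposing the week-6 comparison could also cost power: 64% against 69/77/90% with adjustment when week 0 is unaffected.

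Any bias is plausible only for the secondary CFU/g outcome and is of unknown size and sign. The open points are the order of allocation, first session and biopsy, and the contrast tested for each tissue outcome. They are missing detail that analysts hold and would ordinarily report. The figures rest on assumed SDs, correlations and immediate differences. The conclusion that the choice is a trade-off follows from the identity D6 − D0 and from post-session sampling at both visits.

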### 2.5. Outcome Measures

**2.5.1. Main Outcome Measure: Cellular Proliferation Analysis of Wound Tissue Samples.** The same senior clinician interpreted all samples to evaluate the cellular proliferation. The microvascular structure of CD31, an endothelial marker, was subjected to immunohistochemical analysis and quantification to understand the effects of debridement on neo-angiogenesis, [22]. Sections of tissue sample were immunohistochemically stained with the CD31 marker. Light microscopy was used to count the number of microvessels/endothelial cells in a standardized grid, with the results expressed as microvessel density (Leica DMD 800 morphometric system). Microvessel density was scored in proportion to the following scale: 0 (absent), 1 (low, at least one microvessel), 2 (moderate) and 3 (more than two microvessels).

To differentiate collagen content from other components, such as muscle fibrin and erythrocytes, in tissue samples we used Massons's trichome staining. Collagen content was scored according to the following scale: 0 (absent), 1 (mild), 2 (moderate) and 3 (severe) [23].

Actin staining was used to evaluate the presence of myofibroblasts involved in wound healing. These cells increase in number during wound healing. The number of stained cells was semi-quantitatively analyzed using a 0–3 scaling score (0 = no myofibroblasts, 1 = myofibroblasts in low quantities, 2 = myofibroblasts in moderate quantities, 3 = myofibroblasts in high quantities).

**2.5.2. Secondary Outcome Measure: Microbiological Analysis of Wound Tissue Samples** Specimens of wound tissue were homogenized in 0.5 mL volumes of sterile phosphate buffered saline (PBS, Sigma Aldrich, St Louis, MO). After mechanical homogenization, the specimens were seeded in Columbia agar (BD, Sparks, MD), MacConkey agar (BD), Sabouraud dextrose agar (BD) and Columbia

agar supplemented with nalidixic acid and colistin (BD) using a spiral plater Workstation (Don Whitley Scientific, Shipley, UK). Quantitative and qualitative microbiological analyses were performed after incubation of plates at 37 °C for 24 h. Isolated microorganisms were identified by standard methods and susceptibility testing was performed in accordance with Clinical and Laboratory Standards by the disk diffusion method [24]. The results were expressed as CFU per gram of tissue (CFU/g) and the limit of detection was 10 colony-forming units (CFU).

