#### 2.2. Participant

We enrolled patients in which the following inclusion criteria were implemented:

- Male and female patients over 18 years old

Type 1 or type 2 diabetes with levels of HbA1c  $\leq 85.8$  mmol/mol (10%) within 30 days of the beginning of the study, based on a previous international, multicenter, randomized controlled trial [11]

- Wound stages IB, IIB, ID, and IID according to the University of Texas Diabetic Wound Classification [12]
- Wound duration of 1–24 months
- Wound size among 1–30 cm^2 after debridement

- Diabetic foot ulcers showing mild or moderate infection, according to the criteria of the European Wound Management Association (EWMA) [13] and the Infectious Disease Society of America Guidelines [14]
- Ankle-brachial index (ABI)  $> 0.9$  or  $ABI \leq 0.9$  and ankle systolic blood pressure (ASBP)  $\leq 70$  mmHg, or toe systolic blood pressure (TSBP)  $50$  mmHg. In patients with medial arterial calcification (ABI  $> 1.4$ ) we considered Peripheral Arterial Disease (PAD) a toe-brachial index (TBI)  $< 0.7$  [15,16]

We considered exclusion criteria:

- Chronic kidney disease (glomerular filtration rate  $< 60$  mL/min per 1.73 m^2 during at least three months) or dialysis [17]
- Non-treated osteomyelitis
- Necrotizing soft tissue infections
- Critical limb ischemia patients with ABI  $< 0.5$  and ASBP  $< 70$  mmHg or  $< 50$  mmHg [15,16]

Life expectancy  $< 6$  months due to malignant DFU

- Pregnancy and lactation
- Patients diagnosed with human immunodeficiency virus (HIV) or hepatitis
- Patients showing local or systemic conditions that could impair tissue regeneration.

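### The CD31 classes are ambiguous as worded, and section 2.10 does not fix the form, test or time point for the main-outcome markers

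*Combined protocol and SAP*

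**What the plan says.** Section 2.5.1 puts three markers under one main outcome: CD31, collagen and actin. None is singled out. Collagen and actin exist only as 0-3 scores. CD31 appears in two forms. First it is counted: "Light microscopy was used to count the number of microvessels/endothelial cells in a standardized grid, with the results expressed as microvessel density". Then "Microvessel density was scored in proportion to the following scale", with classes "0 (absent), 1 (low, at least one microvessel), 2 (moderate) and 3 (more than two microvessels". No grid area or number of fields is given, and the counted unit is either vessels or endothelial cells.

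Section 2.4.2 gives two biopsies per patient: "Soft tissue punch biopsies (3 mm) were taken after wound debridement sessions at week zero (day 0) and week six (day 42".

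Section 2.10 allots tests by type of variable only. For categorical variables: "Chi-square test was performed to calculate differences between groups and, if applicable, Fisher's exact test for categorical variables". For quantitative ones: "Student's t-test and Mann-Whitney U test were performed for normally and abnormally distributed quantitative variables, respectively". It does not say which type a 0-3 score is. Its only mention of the main outcome concerns plots: "Graphics to evaluate the differences among decrease in bacterial load and cellular proliferation between groups". It names no baseline adjustment and no rule for three markers.

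Section 2.9 states that outcome adjudicators were not blinded. The opening section dates the document 20.01.2020, after enrolment to December 2019, and says that registration was retrospective.

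**The concern.** Two things are at stake.

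The first is freedom of choice. A reader who follows the plan can reach the main result by several routes, each consistent with the text: CD31 as density or score, a 0-3 score as categories or as ordered values, and week 6 or change. Where readers and adjudicators know the arm, a fixed analysis is a main safeguard against picking the favourable route, and here the route is not fixed. This holds whatever the vessel counts were.

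The second is loss of information. Chi-square and Fisher ignore the order of the classes. On the likely reading of the CD31 scale, 3 vessels and 30 vessels score the same. The cap concerns CD31 only; the choice of test concerns all three 0-3 scores, and the choice of time point all three markers.

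**Working it through.** **Class wording.** Which classes does each count satisfy?

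| Vessels | Literal wording | Likely reading |
|---|---|---|
| 0 | 0 | 0 |
| 1 | 1 | 1 |
| 2 | 1 (class 2 only by elimination) | 2 |
| 3 or more | 1 and 3 | 3 |

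The overlap disappears on the likely reading. The cap at three does not.

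**False positives.** The plan gives no figure to reproduce, so this is a simulation. From section 2.7: 24 and 27 patients and alpha 0.05, taken here as two-sided. Assumed: no true effect; class shares 10/40/35/15% or 25% each; latent week 0 to week 6 correlation 0.3, 0.5 or 0.7; 20,000 replicates; Mann-Whitney by the tie-corrected normal approximation. Share of trials in which the smallest p-value is below 0.05, for one 0-3 score:

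| Tests to choose from | False positives |
|---|---|
| Mann-Whitney, week 6 or change | about 8-10% |
| plus chi-square at week 6 | 11-12% |
| plus chi-square on change | about 14% |

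Fisher and the t-test, which section 2.10 also lists, were not included, so these figures do not cover every route in the plan.

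**Power by form and test.** Assumed Poisson counts, score = min(count, 3), 24 vs 27:

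| Mean vessels, surgical vs UAW | Count, Mann-Whitney | Score, Mann-Whitney | Score, chi-square |
|---|---|---|---|
| 1 vs 2 | 80% | 79% | 62% |
| 4 vs 6 | 86% | about 43% | about 26% |

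The Poisson shares in the top class explain the pattern:
- Mean 1: 1 − e⁻¹(1 + 1 + 0.5) = 8%.
- Mean 2: 1 − e⁻²(1 + 2 + 2) = 32%.
- Mean 4: 1 − e⁻⁴(1 + 4 + 8) = 76%.
- Mean 6: 1 − e⁻⁶(1 + 6 + 18) = 94%.

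At 4 vs 6 most patients in both arms sit in class 3. With sparse vessels the choice of test costs more than the cap (79% to 62%, against 80% to 79%). With dense vessels the cap costs more (86% to 43%).

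**Time point.** Assume equal variances and a week-6 test with 80% power. The standardised effect is then 0.786, and z = 0.786 / √(1/24 + 1/27) = 0.786 / 0.2805 = 2.80. Power is Φ(z − 1.96). For change, z is divided by √(2(1 − ρ)). For a week-6 comparison adjusted for week 0, it is divided by √(1 − ρ²). If the week-0 punch already shows a quarter of the effect, z is multiplied by 0.75 for change and by (1 − 0.25ρ) for the adjusted comparison.

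| Assumed ρ | Week 6 | Change | Adjusted | Change, quarter effect at week 0 | Adjusted, quarter effect at week 0 |
|---|---|---|---|---|---|
| 0.3 | 80% | 66% | 84% | 43% | 78% |
| 0.5 | 80% | 80% | 90% | 56% | 81% |
| 0.7 | 80% | 95% | 98% | 77% | 90% |

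The time point therefore matters as much as the test. The quarter is an assumption; section 2.4.2 supports only the timing of the punch.

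**Three markers.** Even with one test per marker, three tests at 5% give 1 − 0.95³ = 14.3% if the markers are independent. Fixing the test alone does not settle the error rate of the main outcome.

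**The case against.** The scale fault is largely one of wording. The label for class 1 (low) and the threshold for class 3 point to 0, 1, 2 and 3 or more, and on that reading nothing overlaps. This stands: a reader might infer that the scale is unusable, and the text does not support that. A clarification is enough, though the cap remains.

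The density-or-score question may be less open than it looks. Section 2.5.1 runs from count to density to score, and the other two markers are only scored, so the score is a plausible analysed form. This also stands in part, because section 2.10 does not confirm it. If density was tested, there is no cap loss at all.

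The 14% needs chi-square on change, where a 0-3 score gives up to seven categories. That is an unlikely choice; 11% to 12% applies without it.

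The power figures rest on assumed counts and do not describe this trial. That is right. A reader might infer that the cap halved this trial's power; the documents report no counts, so the trial cannot be placed between the two rows.

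Section 2.10 does have a rule by variable type, and its graphics sentence mentions a decrease. Neither closes the gap. A 0-3 score fits both types, and the decrease most naturally belongs to bacterial load and describes plots only.

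Finally, a reader might infer that a favourable analysis was picked. Nothing in the documents shows that.

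**Conclusion.** The concern holds in a limited form. The CD31 classes are ambiguous as worded, with a likely reading that removes the overlap but caps the score at three vessels. Section 2.10 leaves open the form of CD31, the test for the three 0-3 scores, and the time point for all three markers. With unblinded adjudicators, the main result is open to choice.

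The size is a false-positive rate of 8% to 14% for one 0-3 score if the smallest p-value were reported, depending on how many routes are counted and under the assumed shares and correlations. The cost of an order-blind test (79% to 62% power at 1 vs 2 vessels) and of the cap (86% to about 43% at 4 vs 6) are illustrations under Poisson counts, not estimates for this trial. The gap in the text is certain; its effect on the trial's result is not known. It should be corrected, with medium confidence in its practical weight.

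**What to change.** - State the CD31 classes as 0, 1, 2 and 3 or more vessels, or give the reading actually used. Add the counted unit and the grid area.
- For all three markers, compare the week-6 value between arms by Mann-Whitney, which section 2.10 already lists, and not by chi-square or Fisher.
- For CD31, analyse the counted density if raw counts were kept, with the 0-3 score beside it. Otherwise analyse the 0-3 score as ordered.
- Report the probability that a UAW patient has the higher value than a surgical patient, with a 95% confidence interval.
- Give an analysis adjusted for the week-0 value as supporting. Its power is often better, but the week-0 punch follows the first debridement and may already carry part of the effect, so it should not lead.
- Either name one marker as lead or apply Holm across the three.
- Label these choices as made after enrolment ended, and as post hoc if results had been seen.

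The cost is a few sentences in the SAP and little extra analysis; no new patients are needed. There are three downsides. The choices cannot be presented as pre-planned. The count analysis depends on raw counts having been kept. Holm makes the thresholds stricter: the smallest p-value is judged against 0.05/3 = 0.0167, the next against 0.05/2 = 0.025 and the last against 0.05.
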